6.3 Analyses Addressing Primary Study Endpoint

The following statistical approaches apply to all study endpoints outlined in Section 3.

Baseline data analyses. Baseline characteristics and proportion of missing data will be summarized for each study arm. If necessary, single imputation will be used to impute values for missing observations as described in Section 5.4. Covariate balance will be assessed using standardized differences (mean or proportion differences for continuous and binary outcomes, respectively). [17] Balance between study arms will be assessed before and after PS matching.

Propensity score model for the arm assignment. A stratified PS model procedure will be used. Strata will be defined by baseline prior exposure to TNFi treatment (e.g. TNFi-naive and TNFi-exposed). Within unique combinations of subgroup strata logistic regression models will be used to estimate the probability of being assigned to the PrismRA arm using pre-treatment covariates and/or missing data indicator variables. All covariates used to estimate the PS will be measured before initiation of study treatment and are listed in Table 4 of Section 6.2. Inclusion of non-linear terms (e.g., transformations, restricted cubic splines) and variable interactions will be considered on the basis of balance diagnostics and subject matter expertise. The PS model will be fit without using outcome information to avoid selection of a model that leads to a favorable treatment effect estimate. [18] If model convergence issues (e.g. model non-convergence warnings or failures) arise, the PS will be re-estimated using the full eligible cohort. Evaluation of the PS model will rely on the ability of the PS to achieve covariate balance between the PrismRA arm and the external control arm. [19] Covariate balance will be described using standardized differences. Standardized differences greater than 0.1 indicate “meaningful” residual imbalance in the corresponding covariate and indicate the need for further refinement of the PS model. [20] In matched analyses, F tests for equality of variances for continuous variables will be used. [17] Graphical summaries of balance will include boxplots, Love plots [21], and empirical density functions of the distribution of covariates in the PrismRA arm and the external control arm. The distribution and overlap of propensity scores among individuals in the PrismRA arm and the external control arm will be examined graphically.

Propensity score matching. Patients in the external control arm will be PS matched with participants in the PrismRA trial arm within strata.[22] Individuals will be matched on the logit-transformed PS using an optimal nearest-neighbor without replacement method within calipers.[23] Optimal matching will be used to minimize the total absolute difference in the logit PS across all matches. [24] Caliper widths will be determined based on the SD of the logit of PS (e.g., $0.2 \times \text{SD}$). [25 26] In order to avoid excluding unmatched PrismRA patients an upper limit

of the caliper width (e.g. $0.3 \times \text{SD}$ of the logit PS) will be specified before expanding the historical control period (as described in Section 5.2). Each PrismRA arm subject will be matched with between one and three external control arm subjects using a variable matching ratio, and the targeted total number of matched external control arm subjects will be approximately twice the size of PrismRA arm. [27] Matched external control arm patients will be further weighted based on the following principle: if a PrismRA arm patient is matched to x controls, then these matched controls will be assigned $w = \frac{N_c}{xN_t}$, where N_t is the total number of matched PrismRA patients and N_c is the total number of matched control patients. Propensity score matching is used to estimate the average treatment effect for the treated (ATT), which provides an estimate of the treatment effect among patients who ultimately received treatment. [16]

Imputation of missing outcome data. All eligible patients meeting inclusion and exclusion criteria and initiating the study treatment will be included in MI models for handling missing outcome data as specified in Section 5.4.

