5.0 GENERAL STATISTICAL CONSIDERATIONS

5.1 Sample Size and Power Calculations

The study is powered to detect a difference of 10% in the proportion of patients with improvement in CDAI from baseline to Week 24 by at least the MID as defined in Section 3.1 between the PrismRA arm and the external control arm. Results are shown in **Table 1**. It is estimated that the attrition rate at Week 24 (defined as the proportion of patients with missing CDAI scores at Week 24 for any reason) can be up to 45% in the PrismRA arm and up to 50% in the external control arm. The sample sizes below have been inflated accordingly to account for the patient attrition mentioned above.

With a sample size of 600 in the PrismRA arm and 1,500 in the external control arm, the study has 88% power to establish the superiority of the PrismRA intervention as compared to the standard of care by detecting a difference of 10% between the two study arms based on Fisher’s

exact test of independent proportions assuming the proportion of patients with improvement in CDAI by MID are 40% and 30% in the PrismRA arm and the external control arm, respectively.

Table 1. Study power for comparing proportion of patients with improvement in CDAI from baseline by at least MID between the two study arms

Sample size in the PrismRA arm before attrition	Sample size in the external control arm before attrition	Proportion of patients in the PrismRA arm with MID improvement in CDAI	Proportion of patients in the external control arm with MID improvement in CDAI	PrismRA arm, attrition			
				30%	35%	40%	45%
				Study power			
600	1,000	0.45	0.35	86%	84%	82%	80%
600	1,000	0.40	0.30	87%	86%	84%	82%
600	1,000	0.35	0.25	90%	89%	87%	85%
600	1,500	0.45	0.35	91%	90%	88%	86%
600	1,500	0.40	0.30	92%	91%	89%	88%
600	1,500	0.35	0.25	94%	93%	92%	90%
600	2,000	0.45	0.35	93%	92%	90%	88%
600	2,000	0.40	0.30	95%	93%	92%	90%
600	2,000	0.35	0.25	96%	95%	94%	92%

The sample size calculation was performed with SAS (version 9.4, Cary, NC).

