5.3 Data Summarization and Analysis

Summary statistics for continuous variables to be reported will include mean, median, standard deviation (SD), 25th and 75th percentile. Categorical variables will be reported using counts and proportions. Hypothesis testing will be two-sided with an alpha level of 5%. For all outcome measures, point estimates as well as two-sided 95% confidence intervals (CIs) will be provided. P-values will be reported where appropriate to four decimal points unless all p-values in a table are greater than 0.01 in which case p-values will be reported to three decimal points in that table as the fourth decimal point is not needed. Details of the specific analytic methods are described below (Section 6).

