6.3.1 Main Analysis

Main analyses will proceed according to the following order of procedures:

- 1) Perform single imputation for all missing pre-treatment covariates.
- 2) Estimate the probability of treatment with PrismRA for matching. Only pre-treatment covariates will be included as predictors of treatment (e.g., blinded to outcomes).
- 3) Perform stratified PS matching and describe patient characteristics of this single matched cohort. Matched external control arm should be weighted following the principle in Section 6.3 before describing patient characteristics.
- 4) Impute missing outcome data using MI as described in Section 5.4.
- 5) Within each imputed dataset, fit treatment effect outcome model with arm assignment as the independent variable with covariates adjustment.
- 6) Pool treatment effect estimates using Rubin's rule.

Steps 1-4 will be performed once at the start of analyses for each analysis population. Steps 5 and 6 will be repeated for each study endpoint and for the Treatment Policy Strategy and Composite Strategy.

Outcome regression models may also include direct adjustment for important patient covariates (e.g. age, sex, race/ethnicity, RDCI, baseline scores). In general, these methods improve confounding control in cases of imperfect matching and stratification. [30] The proportion of patients within each study arm with moderate or high disease activity at baseline who achieve an MID in CDAI of ≥ 6 (baseline moderate) or ≥ 12 (baseline high) at 24 weeks after study treatment initiation will be reported. Odds ratio and 95% CI will be estimated using weighted logistic regression.

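### The 88% power assumes 1,500 equally weighted controls, but the SAP targets about 1,200 matched controls with unequal weights, which gives about 82–86% under the plan's own assumptions

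*SAP*

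**What the plan says.** The power statement in SAP 5.1, repeated in Protocol 10.1, is made for these numbers: "With a sample size of 600 in the PrismRA arm and 1,500 in the external control arm". The claim attached to that size is that "the study has 88% power to establish the superiority of the PrismRA intervention". It rests on Fisher's "exact test of independent proportions assuming the proportion of patients with improvement in CDAI by MID are 40% and 30"%, and attrition "can be up to 45% in the PrismRA arm and up to 50% in the external control arm" is the only reduction applied to the sample sizes. SAP 5.3 sets the level: "Hypothesis testing will be two-sided with an alpha level of 5"%.

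The analysis is described elsewhere. Under propensity score matching, SAP 6.3 says: "Each PrismRA arm subject will be matched with between one and three external control arm subjects using a variable matching ratio". It sets the target number of matched controls at about twice the PrismRA arm and gives each control in a set of x the weight Nc/(x·Nt), where Nc and Nt are the matched control and PrismRA totals. SAP 6.3.1 then states: "Odds ratio and 95% CI will be estimated using weighted logistic regression". SAP 6.4.1 uses weighted least squares for the change in CDAI.

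Neither document gives the expected mix of 1:1, 1:2 and 1:3 sets, a design effect, or a variance estimator for the weighted models. They also describe the 1,500 differently. Protocol 6.2 expects that many after the propensity score step; SAP 5.2 expects that many eligible patients and does not mention that step.

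**The concern.** The power calculation and the analysis do not describe the same control arm, in two respects.

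- **Head-count.** Twice 600 is 1,200 matched controls, not 1,500.
- **Weights.** At an average of two controls per patient, a control in a 1:1 set has weight 2, one in a 1:2 set has weight 1 and one in a 1:3 set has weight 2/3. Unequal weights carry less information than the same number of equally weighted patients.

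The power quoted for the superiority claim may therefore not be what the matching plan delivers.

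A related gap concerns the standard error. The weights sum to Nc, so a model-based standard error treats the weighted controls as Nc full patients. Where that standard error is used without other variance components, the interval can be too short. The SAP does not say which standard error it will use.

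**Working it through.** **Inputs.** SAP 5.1: 600 and 1,500 patients, 45% and 50% attrition, response rates of 40% and 30%. SAP 5.3: two-sided 5% level. SAP 6.3: x from 1 to 3, about 2·Nt matched controls, weight w = Nc/(x·Nt). Assumed, because not given: the split of x, and attrition unrelated to set size.

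**Step 1: reproduce the plan's figure.** 600 × 0.55 = 330 and 1,500 × 0.50 = 750. Exact two-sided Fisher power at 40% v 30% is 88.4%. A continuity-corrected arcsine approximation gives 87.5% and matches all nine rows of the 45%-attrition column to the printed percent. The 88% is correct for its inputs.

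**Step 2: effective control number.** A set of x controls adds x·w = Nc/Nt to the sum of weights, so Σw = Nc. It adds x·w² = Nc²/(x·Nt²) to the sum of squares, so Σw² = (Nc²/Nt)·mean(1/x). Hence

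(Σw)²/Σw² = Nt / mean(1/x).

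This equals Nc when every set has the same x and is smaller whenever x varies.

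**Step 3: power at the SAP's 2:1 target.** Nt = 600, Nc = 1,200, 330 PrismRA patients observed, and half of the effective controls observed.

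| Split of 1:1 / 1:2 / 1:3 | mean(1/x) | Effective controls | After 50% attrition | Exact Fisher power | Simulated weighted logistic, robust SE |
|---|---|---|---|---|---|
| 0 / 100 / 0 | 0.5000 | 1,200 | 600 | 85.8% | 86.8% |
| 25 / 50 / 25 | 0.5833 | 1,029 | 514 | 83.8% | 84.5% |
| equal thirds | 0.6111 | 982 | 491 | 83.1% | 83.7% |
| 50 / 0 / 50 | 0.6667 | 900 | 450 | 81.8% | 82.9% |

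**Step 4: separate the two causes.** Going from 1,500 to 1,200 controls at equal weights costs 88.4 − 85.8 = 2.6 points. Unequal weights then cost nothing if every x = 2, and up to 85.8 − 81.8 = 4.0 points at the most uneven split.

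**Step 5: if 1,500 controls stay matched (mean ratio 2.5).** Half 1:2 and half 1:3 gives 600/0.4167 = 1,440 effective controls and 88.1%. A quarter 1:1 and three quarters 1:3 gives 600/0.5 = 1,200 and 85.8%. Weighting alone then costs 0.3 to 2.6 points.

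**Step 6: if matching falls to the 95% level in SAP 5.2.** Nt = 570 and Nc = 1,140. Fisher power is 84.1% if every x = 2, 81.1% for equal thirds and just under 80% for half 1:1 and half 1:3.

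**Step 7: standard errors under the null (30% v 30%).** Complete-case simulation of the weighted log odds ratio (40,000 runs per split) gave two-sided error with a model-based SE of 5.8% (25/50/25), 6.0% (thirds) and 6.4% (half and half). Robust SEs gave 5.0–5.1%. Further complete-case and fully observed runs with model-based SEs gave about 6.0–6.5%. With multiple imputation within each arm, Rubin's rule and the planned 45%/50% missingness, model-based SEs gave about 5.0–5.1%.

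**The case against.** The other side has several sound points.

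- **The 88% is not a miscalculation.** It reproduces. What is missing is a link between the calculation and the matching plan.
- **Weighting is not the whole loss.** A reader might infer that the weights explain the entire fall from 88%. They do not. The head-count accounts for about 2.6 points, and equal ratios would remove the weighting loss altogether.
- **No single figure is derivable.** A reader might take 82–84% as the power of the written analysis. It depends on an assumed split. The written analysis also imputes missing outcomes and may adjust for covariates, and the documents do not allow either effect to be quantified. This stands, so only a range under the plan's own attrition convention is justified. The 88% ignores those features too, so the comparison is like for like.
- **Similar figures are already in print.** The 600/1,000 row of SAP Table 1 shows 82% at 40% v 30% and 45% attrition, and with all 600 matched no split falls below 80%. True, but the superiority statement relies on the 1,500 row.
- **Inflated false positives in the main analysis.** A reader might infer these from the unspecified standard error. The documents do not prescribe a model-based SE, and simulation at the planned missingness showed no inflation after imputation, where the between-imputation variance already reflects the weights. The point stands only for fits without that component.
- **An unweighted test is also written down.** Protocol 10.4 names Pearson's chi-square test but refers to the SAP for details, and the SAP specifies the weighted model.

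**Conclusion.** The concern holds in a limited form. Under the SAP's own 2:1 matching target, its 45%/50% attrition and 600 matched PrismRA patients, power is about 82–86% rather than 88%. About 2.6 points of the fall come from head-count, and between 0 and about 4 more from unequal weights. If 1,500 controls stay matched, power is about 86–88%, so the answer depends on which control number is meant.

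The result rests on an assumed split of matching ratios, the effective-sample-size approximation, complete cases standing in for imputation, no covariate adjustment and no correlation within matched sets. The simulated weighted model agrees with the Fisher figures to within about 1 point.

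The variance gap is real but narrow. A model-based SE gives roughly 6.0–6.5% two-sided error in the complete-case sensitivity analysis (SAP 6.3.2). The material does not support saying that the main analysis exceeds 5%, or that the design is underpowered.

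**What to change.** 1. In SAP 5.1, SAP 5.2 and Protocol 6.2 and 10.1, say whether 1,500 counts eligible or matched controls, and reconcile it with the target of about twice the PrismRA arm in SAP 6.3.
2. State the expected split of 1:1, 1:2 and 1:3 sets, or a plausible range, and compute power at Nt/mean(1/x). At the 2:1 target, report about 82–86% in place of 88%.
3. In SAP 6.3.1, 6.3.2, 6.4.1 and 6.4.2, specify robust (sandwich) standard errors for the weighted logistic and weighted least-squares models, including those that enter Rubin's rule.
4. Report the effective control number next to N in Table 2.1 and in the sensitivity table (Table 4).

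The cost is a few sentences, one recalculated power table and a robust-variance option in SAS. Study conduct does not change. The stated power falls by a few points, and complete-case intervals become slightly wider where ratios vary.

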6.2 Study population

PrismRA arm:

This arm will enroll approximately 600 RA patients at approximately 33 clinical sites who are at least 18 years of age. All patients in the PrismRA arm will undergo PrismRA testing at their first study visit (Visit 1). See Patient Selection Criteria for details.

External control arm:

Patients with RA in the OM1 PremiOM RA Dataset will be selected based on the same eligibility criteria as in the PrismRA arm and adapted for real-world data availability where necessary.

Patients in the external control arm will be balanced with patients in the PrismRA arm using a propensity score model developed with the primary goal of achieving balance in baseline characteristics between the comparison groups. The external control arm is expected to have at least 1,500 eligible patients after propensity score modeling, with no less than 750 patients having CDAI scores at both baseline and Week 24. The data from patients who initiated b/tsDMARDs in the contemporaneous period (March 2022 and onward) and if needed, the recent historical period (6-month to 3-year period prior to March 2022) will be used to maximize the size of the patient pool while minimizing confounding by the potential secular trends in treatment patterns. The smallest historical time window that can provide the planned number of external control arm patients comparable to the PrismRA arm patients will be used. The overlap in propensity score distributions between the external control and trial arms will inform the ultimate sample size.

The data source for the analysis is the OM1 PremiOM RA Dataset within the OM1's Real-World Data Cloud (OM1, Inc, Boston, MA, US). The OM1 Real-World Data Cloud is derived from deterministically linked, de-identified, individual-level health care claims, electronic medical record (EMR), and other data. EMR data are from sources geographically representative of the U.S. population and include medication history and prescription information, laboratory results, and diagnoses as documented by a physician. Additional medical and pharmacy claims data are linked to the clinical data to fill gaps in patients' clinical care. The medical and pharmacy claims contain billing and coding history on inpatient and outpatient encounters from acute care facilities, ambulatory surgery centers, and clinics. The OM1 Real-World Data Cloud includes data from January 2013 to present day.

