8.10 Patient Follow-up

PrismRA arm:

In order to reduce the loss of patients to follow-up, all patients will be asked for their personal contact information and an alternate person's contact information. Patients may be directly contacted by the Investigator or Sponsor/designee in order to support study follow-up. The designated alternate contact person may also be directly contacted in the event the patient cannot be reached.

For patients who are lost to follow-up, Investigator or Sponsor/designee will search available health status databases to determine vital status and cause of death in case of mortality.

External control arm:

To ensure the availability of sufficient quality of data, at least one CDAI measurement during the baseline 3-month period prior to the index date (initiation of b/tsDMARDs) will be required. As needed, we will further require CDAI during the follow-up.

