10.1 Sample size

The study is powered to detect a difference of 10% in the proportion of patients with improvement in CDAI from baseline to Week 24 by at least MID as defined in Section 7.1 between the PrismRA arm and the external control arm. Results are shown in Table 3. It is estimated that the attrition rate at Week 24 (defined as the proportion of patients with missing CDAI scores at Week 24 for any reason) can be up to 45% in the PrismRA arm and up to 50% in the external control arm. The sample sizes below have been inflated accordingly to account for the patient attrition mentioned above.

With a sample size of 600 in the trial arm and 1,500 in the external control arm, the study has 88% power to establish the superiority of the PrismRA intervention as compared to the standard of care by detecting a difference of 10% between the two study arms based on Fisher's exact test of independent proportions assuming the proportion of patients with improvement in CDAI by MID are 40% and 30% in the PrismRA arm and the external control arm, respectively.

Table 3. Study power for comparing proportion of patients with improvement in CDAI from baseline by at least MID between the two study arms

Sample size in the trial arm before attrition	Sample in the external control arm before attrition	Proportion of patients in the PrismRA arm with MID improvement in CDAI	Proportion of patients in the external control arm with MID improvement in CDAI	Study power	Alpha (two-sided)
600	1,000	0.45	0.35	80%	0.05
600	1,000	0.40	0.30	82%	0.05
600	1,000	0.35	0.25	85%	0.05
600	1,500	0.45	0.35	86%	0.05
600	1,500	0.40	0.30	88%	0.05
600	1,500	0.35	0.25	90%	0.05
600	2,000	0.45	0.35	88%	0.05

600	2,000	0.40	0.30	90%	0.05
600	2,000	0.35	0.25	92%	0.05

The sample size calculation was performed with SAS (version 9.4, Cary, NC).

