10.3 Baseline Analysis of the External Control Arm

The OM1 team will identify an eligible pool of patients for an external control arm in the OM1's PremiOM RA dataset.

The baseline study data from the PrismRA arm will be provided by the Scipher Medicine team in a format ready for analysis (fully quality controlled), with a corresponding dataset specification document to help the OM1 team understand the data.

From the pool of the study-eligible RA patients in the OM1 PremiOM RA dataset, the external control patients will be selected based on propensity scores. Analytic approaches which adjust for differences in patient baseline characteristics will be used. These approaches include but are not limited to propensity score weighting, matching and covariate adjustment in a multivariable regression model.

Baseline covariates including the following will be considered (defined in a 6-month window prior to the index date unless otherwise specified elsewhere).

Domain	Variables
Patient Characteristics	
 • Age (calculated from birth year) • Sex • Race/Ethnicity • Geography • Body mass index
Lifestyle	
 • Smoking (current, former, or never smoker)
Comorbidities (based on at least two diagnostic codes at least 30 days apart in the external control arm; based on an additional questionnaire in the PrismRA arm.)	
 • Lung disease • Myocardial infarction • Other cardiovascular • Stroke • Hypertension • Fractures spine, hip, or leg • Depression • Diabetes mellitus

	
 • Ulcer or stomach problem • Fibromyalgia 
The Rheumatic Disease Comorbidity Index (RDCI) will be derived.

RA Related	
 • Duration of RA (Defined as the number of days between the date of the first RA diagnosis code and the index date for the external control arm) • Seropositivity (rheumatoid factor or anti-citrullinated peptide antibody) • CDAI at baseline • Previous use of TNFi (yes, no)
Concurrent RA Medications	
 • Methotrexate • Folic acid • Non-methotrexate major csDMARDs (Sulfasalazine, Leflunomide, Hydroxychloroquine) • Glucocorticoids (with prednisone equivalent dose)

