5.2 Analysis Populations

PrismRA arm:

This arm will enroll approximately 600 RA patients at approximately 33 clinical sites who are at least 18 years of age. All patients in the PrismRA arm will undergo PrismRA testing at their first study visit (Visit 1). See Section 6.1.1 and 6.1.2 for patient inclusion and exclusion criteria for details.

This study will perform analyses for two sets of populations from the PrismRA arm. The first one is the modified ITT analysis population, which consists of patients that initiate the study

treatment at Visit 2. A sub-population of patients who are adherent to the PrismRA test results will also be analyzed. This sub-population will exclude patients who initiated TNFis despite having a PrismRA result indicating a molecular signature of non-response to TNFi therapies.

External control arm:

Patients with RA in the OM1 PremiOM RA Dataset will be selected based on the same eligibility criteria as in the PrismRA arm and adapted for real-world data availability where necessary. Patients in the external control arm will be balanced with patients in the PrismRA arm using a propensity score (PS) model developed with the primary goal of achieving balance in baseline characteristics between the comparison groups. The external control arm is expected to have at least 1,500 eligible patients, with no less than 750 patients having CDAI scores at both baseline and Week 24. Data from patients who initiated b/tsDMARDs in the contemporaneous period (March 2022 and onward) will be used and if needed, the recent historical period (6-month to 3-year period prior to March 2022) will be used to maximize the size of the patient pool while minimizing confounding by the potential secular trends in treatment patterns. The PS model building process will aim to retain the inclusion of as many PrismRA arm participants as possible. If less than 95% of the PrismRA arm is included due to the lack of a matched control or non-overlapping PS, the historical period will be used for identifying external control patients. The smallest historical time window that can retain inclusion of greater than 95% of PS matched PrismRA patients will be used. The overlap in PS distributions between the external control and PrismRA arms will inform the ultimate sample size.

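### The stated 88% power is for 1,500 external controls, but the SAP's matching target is about 1,200, which gives about 85%; the two documents also differ on what 1,500 counts and on the historical-window rule.

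*SAP*

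**What the plan says.** **Power.** Protocol 10.1: "With a sample size of 600 in the trial arm and 1,500 in the external control arm, the study has 88% power". SAP 5.1 repeats it: "With a sample size of 600 in the PrismRA arm and 1,500 in the external control arm, the study has 88% power". Both use Fisher's exact test, 40% vs 30%, two-sided alpha 0.05, and attrition of up to 45% (PrismRA) and 50% (control). The tables have rows for 1,000, 1,500 and 2,000 controls and none for 1,200.

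**Matching.** SAP 6.3: "Each PrismRA arm subject will be matched with between one and three external control arm subjects using a variable matching ratio", without replacement, and "the targeted total number of matched external control arm subjects will be approximately twice the size of PrismRA arm". Matched controls are then weighted inversely to the size of their matched set. SAP 6.3.1 runs the main analysis on this single matched cohort.

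**What 1,500 counts.** Protocol 6.2 expects "at least 1,500 eligible patients after propensity score modeling". SAP 5.2 has the same sentence without the qualifier: "The external control arm is expected to have at least 1,500 eligible patients, with no less than 750 patients having CDAI scores". In both documents the 750 are the patients scored at entry as well as at Week 24.

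**Method of adjustment.** Protocol 10.3 leaves it open: "These approaches include but are not limited to propensity score weighting, matching and covariate adjustment in a multivariable regression model".

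**Historical window.** Protocol 6.2 takes the shortest window that supplies the planned number of comparable controls. SAP 5.2 takes the shortest window that keeps more than 95% of PrismRA patients in the matching. Both put the historical period at 6 months to 3 years before March 2022; Protocol 11.1 says 1 to 3 years.

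**The concern.** A reader takes 88% as the power of the primary comparison. That comparison uses the matched cohort, and the printed 88% needs 750 controls with a Week 24 CDAI. A matched set of about 1,200 leaves 600 at the stated attrition, which is also below the minimum of 750 given in Protocol 6.2 and SAP 5.2.

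Reading 1,500 as the pool before matching does not restore the figure, because a 2:1 target then retains fewer controls than the power calculation used. Reading it as the matched set means 2.5 controls per PrismRA patient, not about two. One of the statements has to change on either reading.

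The window rules bear on more than power. Retention above 95% could be reached with one control per patient, well short of 1,500. The SAP rule could therefore stop at a window that the Protocol rule would extend further back. The two rules can select different controls, in a study that names secular trend in treatment as a risk.

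**Working it through.** **Inputs.** 600 PrismRA patients, 1,500 controls, attrition 45%/50%, rates 40% vs 30%, two-sided 0.05 (Protocol 10.1, SAP 5.1). Matching of 1 to 3 controls with a total of about twice the PrismRA arm (SAP 6.3), so 2 × 600 = 1,200. This last figure is derived; the SAP does not print it.

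**Observed numbers.** 600 × 0.55 = 330; 1,500 × 0.50 = 750; 1,200 × 0.50 = 600.

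**Formula.** Continuity-corrected arcsine approximation to Fisher's test:

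d = arcsin √(p1 − 1/(2n1)) − arcsin √(p2 + 1/(2n2)); power = Φ( d × √(4·n1·n2/(n1+n2)) − 1.96 ).

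**The plan's own figure, 330 vs 750.** d = 0.68317 − 0.58037 = 0.10281 (from unrounded terms); multiplier 30.277; Φ(3.1126 − 1.96) = Φ(1.1526) = **87.55%**, printed as 88%. Exact Fisher by enumeration is 88.42%. The formula reproduces all 9 Protocol cells and 34 of 36 SAP cells after rounding; the two misses are 89.48 (printed 90) and 94.45 (printed 95).

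**The SAP 6.3 target, 330 vs 600.** d = 0.68317 − 0.58055 = 0.10262; multiplier 29.182; Φ(2.9948 − 1.96) = Φ(1.0348) = **84.96%**. Exact Fisher is 85.85%.

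| Rates | Printed, 1,500 | Arcsine, 1,500 | Arcsine, 1,200 | Exact Fisher, 1,200 |
|---|---|---|---|---|
| 45% vs 35% | 86% | 85.74% | 83.01% | 84.16% |
| 40% vs 30% | 88% | 87.55% | 84.96% | 85.85% |
| 35% vs 25% | 90% | 90.02% | 87.69% | 88.58% |

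Over the 12 SAP cells for 1,500 controls (three rate pairs, PrismRA attrition 30% to 45%), the loss in moving to 1,200 is 2.04 to 2.74 points.

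**Incomplete matching.** If 95% of PrismRA patients are matched: 570 and 1,140, so 314 vs 570 observed, and power 83.1%.

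**Weighting.** Control weights are proportional to 1/x, where x is the number of controls in the matched set. Effective controls = (Σw)²/Σw². Each set's weights sum to 1, so Σw = 600, and each set adds 1/x to Σw². The documents do not give the mix of ratios, so a range is shown for a mean of two controls (40% vs 30%, 50% control attrition):

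- All matched 1:2: Σw² = 600 × 1/2 = 300; 360,000/300 = 1,200 effective; 85.0%.
- Equal thirds 1:1, 1:2, 1:3: Σw² = 200 × (1 + 1/2 + 1/3) = 366.7; 982 effective; 82.1%.
- Half 1:1, half 1:3: Σw² = 300 × (1 + 1/3) = 400; 900 effective; 80.6%.

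**Lower missingness.** With 1,200 controls and 45%, 40% or 37.5% missing (660, 720 or 750 observed), power is 86.1%, 87.1% or 87.6%.

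**Ceiling on matched controls.** 3 × 600 = 1,800, so the 2,000-control rows cannot occur under the SAP's matching.

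**The case against.** The case for leaving the plan alone has several parts.

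- The tables already bracket 1,200. For 40% vs 30% at 45% PrismRA attrition they print 82% at 1,000 and 88% at 1,500, so a reader could interpolate about 85%. This stands as a reason to call the effect small. It does not make 88% the right headline for a 2:1 target.
- The target is approximate, up to three controls per patient are allowed, and both documents say that propensity score overlap will settle the final size. This stands: 1,200 is not a cap and 1,500 matched controls is possible. But 1,500 is 2.5 per patient, which is not the ratio that SAP 6.3 names.
- The attrition figures are upper limits. With 1,200 controls, power is 88.6% at 35% PrismRA attrition and 89.9% at 30%. Control missingness may also be lower, since Protocol 8.10 says "As needed, we will further require CDAI during the follow-up". Both points are fair, but the 88% is itself stated at the limits, and SAP 5.4 anticipates roughly 45% and 50% missing.
- Within the Protocol alone, 88% is coherent: 1,500 is a count after modelling, and weighting is an allowed method. This stands. The fault is a mismatch between the Protocol and the SAP, and within the SAP between 5.1 and 6.3.
- The 95% retention rule may be a way to put the Protocol's word on comparability into practice. That is possible, but the two rules still stop at different points.

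A reader might infer that the study is underpowered or that the 88% was miscalculated. The documents support neither. The figure is correct for 1,500 controls, and every scenario computed here at the 2:1 target stays above 80%.

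**Conclusion.** The concern holds at modest size. The 88% in Protocol 10.1 and SAP 5.1 does not describe the matched cohort that SAP 6.3 targets. At that target and the stated attrition limits, the plan's own method gives about 85% for 40% vs 30%, 83.0% for 45% vs 35% and 87.7% for 35% vs 25%.

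The 85% assumes that all 600 enrolled patients start treatment and are matched, and it takes no loss for weighting. Shortfalls on either count lower it. All the figures are complete-case Fisher figures, as in the plan. The main analysis uses multiple imputation and weighted, covariate-adjusted logistic regression, so actual power will differ, and any precision gained from covariate adjustment is not counted here.

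The meaning of 1,500 and the window rule are separate inconsistencies of wording. They need settling whatever the power figure, because they determine which controls enter the analysis.

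**What to change.** 1. State in Protocol 6.2 and SAP 5.2 whether 1,500, and the 750 with both CDAI scores, are counted before or after matching. If after, align the SAP 6.3 target with 2.5 controls per PrismRA patient.
2. Otherwise add a 1,200-control row to both power tables and restate the headline as about 85% for 40% vs 30% at 45%/50% attrition. Note that this is a complete-case figure, that it assumes all 600 start treatment and match, and that it precedes any weighting loss. Do not relabel the 1,500 row as a pool size while keeping its printed power, which assumes 750 analysed controls.
3. In the SAP only, mark the 2,000-control rows as unattainable under matching of up to 1:3. Leave the Protocol rows unless matching is made the only method there.
4. Reconcile the window rule and the historical period across Protocol 6.2, Protocol 11.1 and SAP 5.2, so that one rule applies.

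**Cost.** Wording and one added row (three rate pairs) per table; no extra patients. If item 2 applies, the quoted power falls by about 3 points. If the rule based on the number of controls is kept, it may admit older controls, against the stated aim of limiting secular trends.
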